6. PROTOCOL

I. Study Overview and Specific Aims

The proposed multi-center, open-label, longitudinal cohort study aims to capture the safety profile of FMT in recurrent CDI, as well as to contribute additional efficacy data to the existing body of evidence. The proposed study includes collaboration with Investigators who are able to define the microbial landscape of patients pre- and post-FMT, and further elucidate if there is a microbial signature that predisposes patients to respond, fail treatment, or have adverse events from FMT.

Study Title

Safety of fecal microbiota **T**ransplantation: **O**penBiome **O**utcomes and **L**ongitudinal follow-up (STOOL) for recurrent *Clostridium difficile* infection

Specific aims (SA)

SA1. Determine the short-term (<6 weeks) safety of FMT for the prevention of further CDI recurrence.

Hypothesis: Careful donor screening for both infectious and non-infectious yet potentially microbiome-associated conditions minimize the risk of donor to recipient transmission of disease. Therefore, FMT will not be associated with meaningful number of *related* serious adverse events, recognizing that the recurrent CDI patient population is conventionally elderly with multiple comorbidities and may be at risk for FMT procedure-related complications compared to otherwise young and healthy individuals based on conventional literature.

SA2. Determine the long-term (6-12 months) safety of FMT for the prevention of further CDI recurrence.

Hypothesis: Careful donor screening for both infectious and non-infectious yet potentially microbiome-associated conditions minimize the risk of donor to recipient transmission of disease. Therefore, FMT will not be associated with meaningful number of *related* serious adverse events, recognizing that the recurrent CDI patient population is conventionally elderly with multiple comorbidities and may be at risk for developing new conditions, new medications or adverse events including death, but unrelated to FMT material.

SA3. Determine the longitudinal robustness of FMT clinical cure rate for the prevention of further CDI recurrence.

Hypothesis: We predict a clinical cure rate in keeping with the current literature (80-90%) at the12 month follow-up time interval. This predicted longitudinal response rate would exclude patients who require further antibiotics that put them at risk for CDI reinfection, not true recurrence.

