SA4. Collect pre- and post-FMT stool samples from patients with recurrent CDI as well as donor stools for microbiome analysis.

Hypothesis: Prior to FMT, recurrent CDI patients will have deficiencies of certain normal colonic flora.²² After FMT, these microbial populations will be restored, resulting in a durable transition to a diverse, stable community that resembles the composition of the healthy stool donor. We expect that this transformation will be stable in the absence of challenge with antimicrobial therapy.

II. Subject Inclusion/Exclusion Criteria

Definitions

- **Clostridium difficile infection**: At least 3 unformed stools over 24 hours for 2 consecutive days and either positive stool test (ELISA or PCR) for *Clostridium difficile* toxins or pseudomembranes on colonoscopy (SHEA-IDSA guidelines).²⁶
- **Clinical Cure**: Clinical resolution of diarrhea (<3 unformed stools for 2 consecutive days) with maintenance of resolution at 6-week follow-up period, at minimum, and no further need for antibiotic therapy for CDI. In keeping with SHEA-IDSA guidelines and an absence of 'test of cure,' subjects who meet aforementioned definition will be considered a clinical cure regardless of any incidental follow-up stool testing employed.²⁶
- **Clinical Non-Response:** Ongoing or development of diarrhea and the requirement for antibiotic therapy for CDI.

Inclusion criteria

- Adult (age 18-75 years old)
- Outpatient
- Third or further documented CDI episode and
- Unable to maintain CDI cure after standard therapy with oral vancomycin or fidaxomicin
 - Previous treatment with at least one course of tapered/pulse vancomycin or
 - Inability to taper or stop vancomycin or fidaxomicin without developing diarrhea requiring antibiotic therapy.
- Improvement of CDI symptoms on vancomycin or fidaxomicin

Exclusion criteria

[figure not shown]
- Unable to comply with study follow-up procedures at discretion of MD
- Unable to provide informed consent at discretion of MD
- Participating in another clinical trial
- Pregnant or nursing currently or planned pregnancy in next 1 year
- Evidence of toxic megacolon or gastrointestinal perforation
- Peripheral white blood cell count >30 x 10⁹/L and/or temperature >38 degrees Celsius
- Admission to an intensive care unit within prior 7 days for any reason
- Previously undergone FMT
- Severely immunocompromised patients

- HIV infection (any CD4 count)
- AIDS-defining diagnoses
- Inherited/primary immune disorder

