- Once at the most proximal location, 250 mL of the fecal material will be passed through the endoscope channel using a sterile syringe.

- Standard normal saline flush(s) will be utilized after all the fecal material has been infused.
- 2. Enema
 - The procedure will be completed by a trained Registered Nurse, Physician Assistant, or physician in an outpatient clinic, endoscopy recovery area, or standard endoscopy unit.
 - Fecal material will be transferred into conventional enema bottle/bag.
 - Patient will be placed in left lateral decubitus position with foot of bed elevated to facilitate retention.
 - Lubricated enema nozzle will be inserted into rectum and contents expelled into the distal colon with the subject requested to retain material for at minimum 30 minutes but targeting 1 hour.
 - The patient will be asked to transfer to right lateral decubitus position after 15 minutes. If unable to retain material for 1 hour, total retention time will be recorded.

Baseline assessment and follow-up

1. Subjects will be instructed to contact the clinical team if any symptoms of diarrhea occur or any adverse events occur. Follow-up assessments will focus on capturing any serious adverse events, new medical conditions, or changes in patients' pre-FMT medical conditions since last study contact.

2. After passing eligibility assessment, subjects will be assessed at baseline (Day 0 = day of procedure) to capture and document clinical and FMT characteristics (Appendix 4).

3. A study representative will contact subjects at Day 3 (+/- 2 days) post-FMT (Appendix 4).

4. An in-person clinical assessment between Week 6 (+/- 2 weeks) post-FMT will be performed by FMT provider (Appendix 4). If this visit cannot be arranged, the patient's primary care provider may complete the assessment under the guidance and instruction of the FMT provider.

5. A study representative will contact subjects at Month 6 (+/- 2 weeks) and Month 12 (+/- 2 weeks) post-FMT (Appendix 4).

6. A study representative will contact subjects to remind them to collect and mail stool samples.

7. A full Subject Contact Schedule (Appendix 5) and Informed Consent (Appendix 6).

In the event of clinical non-response

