1. Colonoscopy/sigmoidoscopy: If patients experience clinical non-response and require vancomycin/fidaxomicin within 6 weeks post-FMT, after a 10 day course subject may opt to undergo a second FMT via colonoscopy with an alternate donor at the physician's discretion. Subjects will be followed per protocol for duration of study.

2. Enema: If patients experience clinical non-response and require vancomycin/fidaxomicin within 6 weeks post-FMT, after a 10 day course subject may opt to undergo a second FMT via colonoscopy with an alternate donor at the physician's. Subjects will be followed per protocol for duration of study.

Withdrawal

- 1. All reasons for study withdrawal will be reported.
- 2. Classification of withdrawal:
 - Post-enrollment but pre-FMT
 - Post-FMT but lost to follow-up at:
 - o Day 3
 - o Week 6
 - o Month 6
 - \circ Month 12
 - All reasonable efforts will be exhausted to contact subjects, and data analysis will be based on the last available assessment.
 - Adverse event or serious adverse event mediating withdrawal
 - Rescind informed consent
 - Procedure-related ineligible patients
 - Patients undergoing colonoscopy/sigmoidoscopy and discovered to be ineligible due to newly discovered exclusionary criteria (eg. in-situ colorectal cancer). FMT will not be performed as part of this study and no data will be collected.

V. Study Observations and Measurements

Study Endpoints

Safety Endpoints

Safety will be assessed by short and long-term safety summaries classified into:

- 1. Serious Adverse Events (SAE)
- 2. Adverse Events (AE)
- 3. New medical conditions
- 4. Changes in pre-existing medical conditions

Efficacy Endpoints

Efficacy will be captured through:

- 1. Clinical cure rate of first FMT at 6-week follow-up
 - Colonoscopy
 - Sigmoidoscopy
 - Enema

2. Clinical cure rate of second FMT at 6-week follow-up, in patients with clinical non-response

- Colonoscopy/sigmoidoscopy non-response: Alternate donor FMT by colonoscopy
- Enema non-response: Alternate donor FMT by colonoscopy

Microbiome Endpoints

Sequencing data targeting the composition of the gut microbiome will be used to assess whether there are consistent microbial signatures associated with clinical cure, clinical non-response, or safety endpoints.

Data Collection

Case Report Forms will be utilized to capture and collect data (Appendix 4):

1. Baseline Assessment (Day 0 - Clinical Assessment)

Section 1: Clinical Evaluation

- Study patient identifier
- Date

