- Demographics: Age, sex, race/ethnicity
- Pre-existing medical conditions
- Concomitant medications
- Vital signs including height, weight, calculated body mass index (BMI)
- CDI History, including:
 - o Date of initial CDI diagnosis
 - Number of CDI recurrences since initial diagnosis
 - o Baseline clinical symptoms and severity related to CDI
 - CDI treatments received to date

Section 2: FMT Procedure

- Study patient identifier
- Date
- Description of FMT procedures, including:
 - Route of administration (colonoscopy/sigmoidoscopy or enema)
 - Location in colon where FMT delivered
 - Sedation (if applicable)
 - Prep quality (if applicable)
 - Findings of colonoscopy (if applicable)
- Dose
- Unit ID/Lot# of each treatment
- Expiration Date
- Storage Condition
- FMT retention time (if less than 1 hour)
- Immediate adverse events

2. Short-term assessment I (Day 3 – Telephone Assessment)

- Study patient identifier
- Date
- Any change in baseline clinical symptoms related to CDI
- Assessment of SAEs, including:
 - Any complications related to FMT administration
 - Any potential infectious complications such as transmissible enteric infections, sepsis, peritonitis, or bacteremia
 - Any non-serious newly diagnosed infections (specific organism and body site)

- Any new medical conditions / new medications with associated clinical course
- Any changes in pre-existing medical conditions with associated clinical course
- 3. Short-term assessment II (Week 6 Clinical Assessment)
 - Study patient identifier
 - Date
 - Vital signs including height, weight, calculated body mass index (BMI)
 - Any change in baseline clinical symptoms related to CDI including documentation of clinical cure or clinical non-response
 - Assessment of SAEs, including:
 - Any complications related to FMT administration
 - Any potential infectious complications such as transmissible enteric infections, sepsis, peritonitis, or bacteremia.
 - Any new non-serious diagnosed infections (specific organism and body site)
 - Any new medical conditions / new medications with associated clinical course
 - Any changes in pre-existing medical conditions with associated clinical course

4. Long-term assessment I (Month 6 – Telephone Assessment)

- Study patient identifier
- Date
- Self-reported height and weight, resulting calculated BMI
- Any recurrence of CDI with description of clinical course, including additional treatments received
- Assessment of any new SAEs

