4. We will minimize the risk of severe CDI recurrence by maintaining close clinical contact with all subjects. Subjects will be encouraged to contact the clinical team if they experience recurrence of diarrhea, fever, or abdominal pain – so that stool can be tested for *C. difficile* toxin if indicated, and antibiotics can be resumed if necessary. Subjects will be contacted via telephone by a Clinical Research Coordinator on Day 3, Week 6, Month 6 and Month 12. A clinical assessment will take place between Week 6 +/- 2 weeks. If any patient experiences recurrent CDI via FMP250 or FMP250E they would be eligible for a second FMT by colonoscopy using a different donor.

VII-E. Safety Monitoring Protocol

Safety monitoring plan

An external Data and Safety Monitoring Board (DSMB) will be assembled to evaluate the data and the safety of subjects enrolled in the study. The DSMB will consist of 3 physicians with specialization in gastroenterology and/or infectious disease. Initially, the Board will convene with the Principal Investigator to review the study protocol and guidelines for data and safety monitoring. This initial review will include establishing standard procedures for monitoring. At each quarterly meeting the DSMB will evaluate recruitment, the progress of the study, subject retention, data quality and confidentiality. The DSMB will review subjects' clinical status, adverse events and whether or not there have been any changes in risk to participating subjects. This quarterly review will ensure that subject risk does not outweigh study benefits. A report generated from each of these meetings will be retained at the study sites and will be forwarded to the IRBs and to the FDA (in accordance with Investigational New Drug (IND) regulations). The DSMB will be available to convene outside of the appointed meeting schedule if necessary, due to concerns regarding a particular subject, or due to any adverse events during the study. The DSMB will make appropriate recommendations for changes in the study protocol, if needed.

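### The rule for subjects lost after FMT is tied to no endpoint, so the cure rate depends on how it is read; safety rates have no stated denominator or interval

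*Combined protocol and SAP*

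**What the plan says.** All references are to Section 6 of the combined protocol and SAP.

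- **Lost subjects (IV, Withdrawal).** After the list of time points at which a subject may be lost, the only analysis rule is that "data analysis will be based on the last available assessment". No endpoint, time point or denominator is named.
- **Cure (II, Definitions).** Cure is resolution of diarrhea "with maintenance of resolution at 6-week follow-up period, at minimum, and no further need for antibiotic therapy for CDI".
- **Non-response (II, Definitions).** "Ongoing or development of diarrhea and the requirement for antibiotic therapy for CDI".
- **Where status is recorded (V, Data Collection).** Cure or non-response is documented on the Week 6 form. The Day 3 form records only change in CDI symptoms.
- **Steps that limit missing status.** If the Week 6 visit cannot be arranged, the "primary care provider may complete the assessment under the guidance and instruction of the FMT provider" (IV). Section VII-D adds: "Subjects will be contacted via telephone by a Clinical Research Coordinator on Day 3, Week 6, Month 6 and Month 12". The Month 6 and Month 12 forms ask for "Any recurrence of CDI with description of clinical course, including additional treatments received".
- **Month 12 (I, SA3).** "We predict a clinical cure rate in keeping with the current literature (80-90%) at the12 month follow-up time interval". The aim adds: "This predicted longitudinal response rate would exclude patients who require further antibiotics that put them at risk for CDI reinfection".
- **Analysis (V, Data Analysis).** Cure rates, unweighted and DerSimonian-Laird pooled, get a 95% confidence interval. Safety gets event counts and crude rates for the whole cohort, with no interval and no stated denominator. Section X repeats that the focus is on counts and rates of serious adverse events.

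**The concern.** A subject who is well at Day 3 and is never reached again meets neither definition. Cure needs resolution held to Week 6; non-response needs diarrhea and a CDI antibiotic. The last-assessment rule is the only text on such a subject, and it can be followed in more than one way: count the Day 3 status as cure, leave the subject out, or keep the subject in the denominator as not cured. The choice could be made after the data are seen. The same rule lets a Week 6 cure serve as a Month 12 cure, although durability to Month 12 is what SA3 sets out to measure.

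Safety is a separate gap in the same analysis section. It is the study's overarching objective, and the sample size of 150 was set by recruitment time. An interval is therefore the only way to show what few or zero events can rule out, and the plan gives intervals to cure rates alone.

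The study has one arm and no decision threshold, so what is at stake is the reported estimates.

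**Working it through.** **Inputs.** From the plan: 150 subjects and a predicted cure rate of 80-90% (stated for Month 12, used here as a plausible range). The plan gives no loss rate, so every loss figure below is an assumption. There is no stated figure to reproduce, because 150 has no statistical derivation.

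**1. Week 6 cure, one data set under three codings.** Assume 135 assessed, 115 of them cured, and 15 not assessed, of whom 3 had a documented non-response and 12 were lost while well. Intervals are exact 95%.

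| Coding of the 12 | Calculation | Cure rate (95% CI) |
|---|---|---|
| Last status carried forward as cure | (115 + 12)/150 | 84.7% (77.9-90.0) |
| Known status only, known failures kept | 115/(135 + 3) = 115/138 | 83.3% (76.0-89.1) |
| Unknown = not cured | 115/150 | 76.7% (69.1-83.2) |

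The spread between the extremes is the share lost while well: 12/150 = 8.0 points. With 30 not assessed (6 documented failures, 24 lost while well) and 102 cured of 120 assessed, the figures are 126/150 = 84.0%, 102/126 = 81.0% and 102/150 = 68.0%.

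Known failures must stay in the known-status figure. Dropping the 3 would give 115/135 = 85.2%, which is 1.9 points above 83.3%.

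**2. Inflation from carry-forward.** If a share L is lost while well and a fraction c of them are truly cured, carrying wellness forward adds L(1 - c). At L = 0.10:

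- c = 0.90: 1.0 point
- c = 0.80: 2.0 points
- c = 0.50: 5.0 points

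For scale, the sampling half-width at 85% cure is 1.96 x sqrt(0.85 x 0.15/150) = 5.7 points.

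**3. Second-FMT cure.** If 10-20% do not respond, at most 150 x 0.10 = 15 to 150 x 0.20 = 30 subjects enter this endpoint. One subject of unknown status moves it by 1/15 = 6.7 to 1/30 = 3.3 points.

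**4. Month 12 cure (SA3).** If 10-20% are lost after Week 6 and 5-15% of those recur later, using Week 6 cure in place of Month 12 cure adds 0.10 x 0.05 = 0.5 to 0.20 x 0.15 = 3.0 points.

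**5. Zero safety events.** The exact two-sided 95% upper limit is 1 - 0.025^(1/n).

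- n = 150: 2.43%
- n = 120 (20% not followed): 3.03%

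The plan as written would report neither limit.

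**The case against.** **The definition of cure already bars the carried-forward reading.** Cure requires resolution at Week 6 and is documented only on the Week 6 form, so the 84.7% figure is one that the protocol's own definition speaks against. This has weight, and a reader should not infer that the plan instructs analysts to count Day 3 wellness as cure. But the Withdrawal sentence is unqualified, and nothing says that the definition prevails. If it does prevail, the denominator remains open: 83.3% or 76.7% in the illustration.

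**Follow-up is layered.** Subject call-in, the primary care option, the Week 6 call and the later recurrence histories will resolve many cases. They make the group smaller. The protocol itself still lists loss at Week 6 as a category.

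**Month 12 cure is an SA3 hypothesis and not a listed efficacy endpoint.** That is correct, and the assumed effect there is small. The rule still lets an earlier status answer a durability aim.

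**The effect is modest.** If the lost resemble the rest, 1-2 points lie well inside the 5.7-point sampling half-width. This stands.

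**Stronger safety readings.** A reader might infer that crude rates always understate risk and that person-time recovers the truth. The documents support neither. The plan states no denominator, so a fixed 150 is an assumption, and the result depends on when events occur. Take a true 5% risk in 150 subjects (7.5 expected) and 20% (30) lost just after Week 6:

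- With a constant hazard, h = -ln(0.95) = 0.0513 per year. The crude rate over 150 is 0.8 x 5% + 0.2 x (1 - exp(-0.0513 x 6/52)) = 4.1%, which is low.
- With all events before the loss, the crude rate is 7.5/150 = 5.0%, which is unbiased. A single person-time rate is then 7.5/(120 + 30 x 6/52) = 7.5/123.5 = 6.1 per 100 person-years, which is too high.

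The plan expects procedure-related events early, so the second pattern is realistic.

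**Conclusion.** The point holds and should be fixed. The rule for lost subjects is not limited by endpoint. Followed literally, it conflicts with the definition of cure at Week 6 and lets Week 6 cure stand for Month 12 cure. Set aside, it leaves the denominator unstated.

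In the illustration the reading alone moves the Week 6 cure rate from 76.7% to 84.7%. That range rests on the assumption that 12 of 150 are lost while well, and it shrinks or grows in step with that share. The bias from carry-forward itself is smaller: 1-2 points at 10% lost if the lost match the predicted cure rate, and 5 points if half are cured.

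For safety, the supported statement is narrow: the denominator is not given and no interval is planned, so zero events would be shown without the limit of 2.4% (150) or 3.0% (120). The direction of any bias in the crude rates cannot be settled from the documents.

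**What to change.** **1. Replace the Withdrawal sentence with endpoint-specific rules.**
- A documented non-response or recurrence counts as not cured for that FMT at that and every later time point, even if the subject is then lost. SA3's exclusion for reinfection after further antibiotics stays as it is.
- A favourable status is never carried forward to Week 6 or to Month 12.
- A subject who missed Week 6 (including its window of 2 weeks either side) but is reached later is classified from the recurrence history on the Month 6 or Month 12 form.

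**2. Name the headline before analysis.**
- Use all treated subjects, unknown counted as not cured, with a 95% CI and the same coding for the unweighted and the DerSimonian-Laird pooled rates.
- Report two sensitivity figures: cure among subjects with known status (known failures included), and a best-case bound in which only unknown subjects count as cured.
- Apply the same rules to second-FMT cure and to Month 12.

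**3. Safety.**
- Report subjects with events over the number treated and over the number assessed, separately for the short-term (under 6 weeks) and long-term (6-12 months) windows of SA1 and SA2.
- Give exact 95% CIs, including the upper limit when there are no events.
- Limit any person-time rate to long-term events.

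**Cost.** Only analysis wording changes; no visit or form is added. There is slightly more analysis work, and the headline cure rate will look less favourable (76.7% in the illustration). That headline treats every unknown subject as a failure, and the known-status figure assumes that the lost resemble those seen, so they should be read side by side.
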